6.5.4 Subgroup analysis

We will explore differences in the primary endpoint between the two groups in different subgroups through subgroup analysis. Logistic regression will be used for univariate and multivariate analyses, with effect sizes represented by OR and 95% CI, and interaction P-values will be calculated. The subgroups include:

- Sex: male, female
- Age: ≤ 65 years, > 65 years
- Tumor site: the lower edge of the tumor is above the peritoneal reflection; the lower edge of the tumor is below or at the peritoneal reflection
- Other variables independently associated with primary endpoints in multivariate analysis.

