11.4.4 Subgroup analysis

We will explore the differences in the primary endpoints between the two groups in different subgroups through subgroup analysis. The subgroups include gender (male; female), age (≤ 65 years old; > 65 years old), the relationship between the lower part of the tumor and the peritoneal reflection (above the peritoneal reflection; below the peritoneal reflection), as well as other variables that are independently related to the primary endpoint in the multivariate analysis. Logistic regression will be used for univariate and multivariate analyses, with effect sizes represented by OR and 95% CI, and subgroup interaction P-values will be calculated.

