OR	odds ratios
SAP	statistical analysis plan
FD	free-drainage
LAR	low anterior resectio
RUV	residual urine volume
LOCF	Last Observation Carried Forward
ISR	intersphincteric resection
TCA	Turnbull-Cutait Pull-Through Coloanal Anastomosis
TaTME	total mesorectal excision
ARD	absolute risk differences
CRM	Circumferential Resection Margin
pCR	pathological complete response
DRM	Distal Resection Margin

1 Introduction

The ICCAUT trial is a single - center, prospective, two - arm, parallel - group randomized controlled study. It aims to investigate the effect of the intermittent catheter clamping combined with active urination training (ICCAUT strategy) on urinary retention and secondary catheterization after proctectomy. The aims, hypotheses, and design of the ICCAUT trial are detailed in the protocol. This statistical analysis plan (SAP) focuses on the upcoming analysis and presentation of the trial data. This SAP is based on the study protocol version 2.0. The comprehensive study design, including primary and secondary endpoints, methods for determining sample size, and the approach to data management, are essential parts of the SAP. They are crucial for understanding the trial's methodology and result interpretation.

We develop this statistical analysis plan before completing the enrollment. This helps avoid issues like selection bias in analysis methods and multiple comparisons. These issues could occur if the plan is not determined in advance.

2 Study description

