2.2 Treatment allocation

Patients who meet the inclusion criteria will be randomly assigned to the ICCAUT group or the free-drainage (FD) group. Stratified randomization will be performed based on the following two factors: (1) sex and (2) whether APR was performed. The allocation ratio of the ICCAUT and FD group will be 1:1.

3 Objective

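### Beyond three fixed subgroups, the list is filled by whichever variables predict the outcome in the trial's own data, and APR versus LAR, a randomisation stratum, is not guaranteed a place (minor)

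*SAP*

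**What the plan says.** SAP 6.5.4 names three subgroups for the primary endpoint:

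- "Sex: male, female"
- "Age: ≤ 65 years, > 65 years"
- "Tumor site: the lower edge of the tumor is above the peritoneal reflection", against below or at it

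A fourth entry is open: "Other variables independently associated with primary endpoints in multivariate analysis". Protocol version 2.0, section 11.4.4, has the same three and the same addition: "as well as other variables that are independently related to the primary endpoint in the multivariate analysis". Both sections plan logistic regression with odds ratios and interaction P values. Neither names the analysis set for the subgroups.

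The multivariable model that feeds the open entry is described in SAP 6.5.1. It is fitted in the per-protocol (PPA) set. Treatment group, tumour site, sex and age are forced in, and any other variable with a univariate P value below 0.1 is added.

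On allocation, SAP 2.2 states: "Stratified randomization will be performed based on the following two factors: (1) sex and (2) whether APR was performed". Surgical procedure (LAR/APR) is neither a fixed subgroup nor a forced covariate. It is one row of the univariate table in SAP 6.5.1.

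SAP section 1 says of writing the plan before enrolment is complete: "This helps avoid issues like selection bias in analysis methods and multiple comparisons".

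**The concern.** A subgroup analysis asks whether the treatment effect differs between kinds of patient. The open entry picks variables by a different property, namely whether they predict the outcome. A strong predictor of urinary dysfunction need not change the effect of ICCAUT, and a variable that does change it need not be a strong predictor.

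Two consequences follow. First, nobody can say before the outcomes are analysed how many interaction tests there will be or in which variables, and this sits badly with the aim stated in SAP section 1. Second, the trial balanced its arms on APR by design, yet whether a reader ever sees the effect separately for APR and LAR depends on a significance screen. At stake is how the subgroup table can be read and whether one design stratum appears in it. The primary result is not at stake.

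**Working it through.** The plan gives no figure of its own for subgroups, so there is none to reproduce. The check is a comparison of lists followed by a short calculation.

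**1. Lists side by side.**

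| Role | Variables | Source |
|---|---|---|
| Randomisation strata | sex, APR | SAP 2.2 |
| Fixed subgroups | sex, age, tumour site | SAP 6.5.4 |
| Forced covariates | group, sex, age, tumour site | SAP 6.5.1 |
| Screened at univariate P < 0.1 | all other rows, including LAR/APR | SAP 6.5.1 |

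The stratum missing from the fixed subgroups is APR. To become a subgroup it must pass the screen and then count as independently associated. SAP 6.5.4 sets no threshold for the second step; the only candidate is the general 5% level in SAP 6.1.

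**2. Number of candidates.** The univariate table has 24 variables. Four are forced, so 24 − 4 = 20 are screened. One of these, catheter duration (up to 2 days or longer), can hardly vary in the PPA set, because SAP 6.2.2 excludes patients whose catheter was not removed on the second day. About 19 are effective.

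**3. Chance of adding a subgroup on noise alone.** Assume that no candidate is related to the outcome, that candidates are independent, and that selection is at 5%.

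- 20 candidates: expected number selected 20 × 0.05 = 1.0; chance of at least one 1 − 0.95^20 = 64%.
- 19 candidates: expected number 19 × 0.05 = 0.95; chance of at least one 1 − 0.95^19 = 62%.

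**4. Chance of a false interaction, which is a different quantity.** In the same scenario each unrelated candidate is selected with probability 0.05 and its interaction is then tested at 0.05. Each therefore contributes 0.05 × 0.05 = 0.0025.

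- Present rule, three fixed plus 20 candidates: 1 − 0.95^3 × 0.9975^20 = 18.4%.
- Present rule, three fixed plus 19 candidates: 1 − 0.95^3 × 0.9975^19 = 18.2%.
- Closed list of four: 1 − 0.95^4 = 18.5%.
- Three fixed subgroups alone: 1 − 0.95^3 = 14.3%.

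In this scenario the present rule and the closed list are level.

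**5. Range under the present rule.** The number of tests can be anything from 3 (14.3%) to 3 + 20 = 23, where independent tests would give 1 − 0.95^23 = 69.3%. The upper end needs every candidate to be selected and is a bound, not an expectation.

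**6. Chance that APR is shown.** The documents give neither the APR share nor its effect on the outcome. Assume 360 patients, an APR share of 10 to 30%, about 52% events without APR, and entry at P < 0.05 in a single step. APR would then be selected with probability 5% if it has no effect, 20 to 41% at an odds ratio of 1.5, and 45 to 82% at an odds ratio of 2.0.

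**The case against.** The strongest reply is that little error control is lost. Selecting on a main effect hardly changes the error rate of the interaction test that follows. In a simulation with 180 patients per arm, event rates of 44.7% and 59.3% and no true interaction, the interaction error among selected variables was 3.2 to 4.9%, for odds ratios of 1.0 to 2.0 and variable prevalences of 20% and 50%. A reader might take the 62 to 64% as the chance of a false subgroup finding. It is not, and step 4 shows no gain from the closed list in that scenario. This part of the reply stands in full.

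The calculation is also idealised. Pathological T, N and TNM stage overlap, as do distance from the anal verge and tumour site, and probably the no-anastomosis level and APR, so independence fails. The real rule has two steps, not one at 5%. The figures are illustrative.

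Next, the selection rule is itself written in advance, both sections describe the work as exploring, and interaction P values are planned. A reader might infer that the plan presents these subgroups as confirmatory, but the documents do not say so. The rule is prespecified; the resulting list is not.

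Finally, stratifying on a factor does not oblige a subgroup analysis of it, and the protocol's change log says the list was revised to avoid subgrouping on unnecessary variables. A reader might also infer that APR is excluded. It is not: it is a candidate in the screen, and procedure is reported among the operative characteristics in SAP 6.4.2. What remains is that its appearance as a subgroup depends on the data, and that an open clause does not serve the stated wish to limit the list.

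**Conclusion.** The point holds as a minor one. The subgroup set is partly chosen from the outcome data, by a criterion (prognosis) that does not match the question (effect modification). Its size is unknown in advance, and one of the two randomisation strata is not guaranteed a place.

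The size is a chance of about 62 to 64% of adding at least one data-chosen subgroup when no candidate matters, assuming independence and selection at 5%. The documents do not support a claim of inflated false interactions in that scenario: the figure is about 18% either way. The rate would rise above this under the present rule only if several candidates were truly prognostic and so entered, and the documents give no basis for saying how many would. The primary ITT comparison is not affected.

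**What to change.** In SAP 6.5.4 and protocol 11.4.4, delete the clause that adds independently associated variables. State a closed list of sex, age, tumour site and surgical procedure (APR versus LAR), analysed in the ITT set by randomised group, with interaction P values. Add that any further subgroup will be labelled post hoc.

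The cost is SAP wording and a one-line protocol amendment. Procedure is already recorded on the case report form, so no new data are needed. There are two downsides. Subgroups suggested by the risk-factor model would be reported only as post hoc. One more interaction test is prespecified, which moves the chance of at least one false interaction from 14.3% for three tests to 18.5% for four, if tests are independent.

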6.6 Explorative analysis

We will conduct an exploratory analysis of urinary tract infections. The main focus is to explore the independent related factors affecting urinary tract infections after rectal surgery. The analysis methods include univariate analysis, multivariate analysis, and subgroup analysis.

7 Interim analyses

No interim analyses are planned in this study.

8 Timing of analysis

We will conduct the primary endpoint analysis of the study after all patients have completed their first postoperative month follow-up and will publish the relevant research findings. The results of the exploratory analysis will be published as a post hoc analysis after the publication of the primary outcomes.

9 References

